9.2 Recording of Adverse Events

At each contact with a subject, an Investigator will seek information on adverse events by specific questioning and, as appropriate, by examination. Information on all adverse events will be recorded immediately in the source document, and also in the appropriate adverse event module of the case report

CONFIDENTIAL

form (CRF). All clearly related signs, symptoms, and abnormal diagnostic procedures results should be recorded in the source document, though they should be grouped under one diagnosis.

All adverse events occurring during the study period will be recorded. The clinical course of each event will be followed until resolution, stabilization, or until it has been determined that the study intervention or participation is not the cause. Serious adverse events that are still ongoing at the end of the study period will be followed up to determine the final outcome. Any serious adverse event that occurs after the study period and is considered to be possibly related to the study intervention or study participation will be recorded and reported immediately.

9.3 Relationship of AE to Study

Principal Investigators will determine the relationship of each adverse event to the study procedures or study drug. The relationship will be classified as any of the following:

- Definitely related
- Probably related
- Possibly related
- Unlikely or unrelated

9.4 Reporting of Adverse Events and Unanticipated Problems

The Data Coordinating Center receives notification of Serious Adverse Events (SAEs) via a specific form completed by the investigator and submitted within 24 hours. An assessment of all incoming SAEs is made to determine whether the event needs to be reported to the FDA. The Coordinating Center sends an electronic copy of each Serious Adverse Event Report Form, as well as baseline medical history, medications reported at baseline and follow-up, and other supporting documentation as needed to the Sponsor within 24 hours. The Coordinating Center also sends all AEs to the Sponsor. All SAEs are reviewed by the Sponsor as required by regulation.

9.4.1 Investigator reporting: notifying the study sponsor

Any serious adverse event will be reported to the study Sponsor within 24 hours of the event. To report such events, a Serious Adverse Event (SAE) form will be completed by the Investigator and sent to the Sponsor, via the Data Coordinating Center, within 24 hours. The Investigator will keep a copy of each SAE form on file at the study site. Report serious adverse events to:

Clinical Trials Coordinating Center
Center for Preventive Ophthalmology and Biostatistics
[name]
[name]
[contact]
[contact] (fax)

Within the following 24 hours, the Investigator will provide further information on the serious adverse event in the form of a written narrative. This should include a copy of the completed Serious Adverse Event form and any other information that will assist the understanding of the event. Significant new information for ongoing serious adverse events should be provided promptly to the study sponsor.

9.4.2 Investigator Reporting: Notifying the local IRB

Each Principal Investigator will follow his/her IRB's reporting requirements. The University of Pennsylvania Investigator will report AEs at least annually to the University of Pennsylvania IRB. Investigators will promptly report any unexpected and related AEs to the IRB, including suspected adverse reactions. Other prompt reporting requirements will include: changes, violation, or deviation to the protocol without prior IRB and Sponsor review to eliminate immediate hazard to a study subject, complaint of a subject when the complaint indicates unexpected risks or the complaint cannot be resolved by the research team, breach of confidentiality, and premature completion of the study. For the UPenn site, an unanticipated problem that includes risk to other subjects must be reported to the IRB within 10

CONFIDENTIAL

working days. If an SAE involves death and other subjects are at risk, the UPenn Investigator must submit a report to the UPenn IRB within 3 days.

9.4.3 Sponsor reporting: Notifying the FDA

This protocol is being conducted under an FDA IND. The Sponsor will report all adverse events to the FDA in the Annual Report and all unanticipated, related and serious adverse events to the FDA per regulation.

9.4.4 Sponsor reporting: Notifying participating investigators

In addition to reporting to the FDA, the Sponsor shares SAEs with participating Investigators.

9.5 Unblinding Procedures

The unblinding of the research team will only be performed if there is an emergency or time-sensitive event for which unblinding would help manage the event. In this case, the Coordinating Center will provide documentation of whether the subject received placebo or ALA within 24 hours of the request to the Coordinating Center. If possible, the study subject will remain blinded. However, if deemed necessary and appropriate by both the site investigator and the Sponsor, the subject can be provided documentation of whether he/she received placebo or ALA within 24 hours of this request.

9.6 Monitoring

9.6.1 Data and Safety Monitoring Plan

Phase 1: After a subject has taken a study dose for 5 days, a study physician will contact the subject and do a complete review of systems to document any adverse events. Symptoms reported will be graded as mild, moderate, or severe and this data will be recorded. If a subject does not feel comfortable proceeding to the next higher dose, then that subject will stop participation in the study at that point. If after review of the adverse event(s) (and their quality) that a subject experienced at a particular dose, then the study physician also may stop the subject's participation in the study if there is any safety concern. If 4 or more (out of 15) subjects state that they could not imagine taking a particular dose for 18 months, then that dose will not be used in the Phase 2 Trial. Adverse events, the severity of adverse events, and the percent of subjects that think they could take a particular dose of ALA for 18 months will be reported to the University of Pennsylvania IRB before proceeding with Phase 2. A Data and Safety Monitor (DSM) will also independently review all adverse events as outlined in the DSM Charter.

Phase 2: While each Principal Investigator has safety oversight of the study conducted at their site, there will also be a Data and Safety Monitor (DSM). Review of known risks from ALA has suggested that ALA is relatively safe and well tolerated (see Section 1.2.2). A Drug Safety Monitoring Plan has been developed based on risk.

10 Study Administration, Data Handling and Record Keeping

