3.1.1 Allocation to Interventional Group

Phase 1- Tolerability

For the tolerability test (Phase 1), 15 subjects will each take ALA at doses of 600 mg, 800 mg, and 1200 mg daily. There is no randomization for the tolerability test. The 15 subjects will receive the ALA after consenting to the tolerability study at the Scheie Eye Institute of the University of Pennsylvania.

Phase 2

Screening/Run-In Phase

After the clinician determines the patient meets preliminary eligibility for the trial and the patient signs the consent form, the screening data will be entered into the data management system. Coordinating Center staff will verify the patient is eligible for the study; correction or confirmation will be performed as needed. The Clinical and Scientific Expert and the Scheie Eye Institute Reading Center will also review the patient's information and retinal images to confirm eligibility prior to randomization and complete a form confirming eligibility that is entered into the data management system.

At the screening visit, all subjects will be provided with a postage-paid mailing envelope. Those subjects that do not meet inclusion and exclusion criteria will be contacted and informed that they did not meet all of the screening criteria. Those subjects that are meeting inclusion and exclusion criteria will be instructed to start the 10 day run-in phase, once they receive the medication bottle in the mail. The UPenn Investigational Drug Service will mail a medication bottle with 10 placebo capsules to the subject. The shipment will include instructions for taking the capsules and a form for providing the first and last dates of taking the capsules. After completing the 10 days of the run-in phase, the subject will use the postage-paid mailing envelope to mail back the medication bottle, any remaining contents, and the form to the clinical site. The subject is not informed of whether the study capsules for the run-in phase are placebo or ALA.

CONFIDENTIAL

Subjects who demonstrate compliance by taking $\geq 80\%$ of the provided capsules and mailing the medication bottle within 40 days of the screening visit will be eligible to continue in the study. If an investigator did not receive a mailed medication bottle but believes the subject followed instructions and the medication bottle was lost in the mail, then that subject may get screened again for the study. In this instance, the subject will have to repeat the screening visit and the run-in phase.

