6.2 Study Intervention and Follow-up Phase

15 subjects (ages 65-90) will take 600 mg of oral ALA once daily with a meal for 5 days. This medication will be placed in a red-banded medication bottle (#1) with clear instructions. Each subject will be monitored by the study physician, who will record a history of any side effects or tolerability issues, including a complete review of systems. If well-tolerated, each subject will then take 800 mg of oral ALA once daily with a meal for 5 days. This medication will be placed in a green-banded medication bottle (#2) with clear instructions. Each subject will be monitored by the study physician who will record a history of any side effects or tolerability issues, including a complete review of systems. If 800 mg of oral ALA is well-tolerated, then these subjects will be asked to take 1200 mg of oral ALA daily again for 5 days with a concurrent meal. This medication will be placed in a blue-banded medication bottle (#3) with clear instructions. Each of these subjects will be monitored by the study physician who will record a history of any side effects or tolerability issues, including a complete review of systems. Patients will be contacted by the study physician every 5 days to check on tolerability issues and to determine if the patient can safely proceed to the next dose of ALA.

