8.1 Primary Endpoint

For Phase 1 of this protocol, the primary endpoint is the percent of adverse events that develop in the study group at each studied dose of ALA.

For Phase 2 of this protocol, the primary endpoint is the mean rate of change of the area of GA in the study eye from baseline to 18 months (from the time of randomization) as evaluated by fundus autofluorescence.

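### The Phase 1 dose-exclusion rule does not say how subjects who stop early count for doses they never reached; read literally, it leans toward not excluding the higher dose

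*Combined protocol and SAP*

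**What the plan says.** Section 3.1.1 describes Phase 1 as if every subject completes all three steps: "15 subjects will each take ALA at doses of 600 mg, 800 mg, and 1200 mg daily". Sections 3.1 and 6.2 instead make each step conditional on the one before, for example "If 800 mg of oral ALA is well-tolerated, then these subjects will be asked to take 1200 mg".

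Section 9.6.1 gives two ways of leaving during escalation, and section 11.1 repeats them. The first is the subject's own choice: "If a subject does not feel comfortable proceeding to the next higher dose, then that subject will stop participation in the study at that point". The second is the physician's: "the study physician also may stop the subject's participation in the study if there is any safety concern". The second needs no statement from the subject.

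Sections 8.2, 9.6.1 and 11.1 all give the same exclusion rule. The trigger reads "If 4 or more (out of 15) subjects state that they could not imagine taking a particular dose for 18 months"; the consequence reads "then that dose will not be used in the Phase 2 Trial". Section 8.2 makes the percentage who think they could tolerate each dose a Phase 1 secondary endpoint. Section 8.1 makes the primary endpoint "the percent of adverse events that develop in the study group at each studied dose of ALA", without naming a divisor.

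No section says whether a subject who has stopped is asked about the doses not reached, how that subject counts for them, whether stoppers are replaced, or whether the divisor stays at 15.

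**The concern.** The fixed 15 fits the description in section 3.1.1, where everyone takes every dose. It does not fit the conditional escalation in sections 3.1, 6.2, 9.6.1 and 11.1, where the number reaching a dose can only fall. The numerator consists of statements about a particular dose. A subject who left at 600 mg has no required occasion to make one about 1200 mg, yet remains one of the 15. On the literal wording, a missing answer then has the same effect as a favourable one.

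The missing answers are informative, because those who leave during escalation are likely to be the least tolerant. The error therefore runs one way: the higher the dose, the more likely that intolerance goes uncounted.

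This count is the only numeric tolerability criterion bearing on which dose goes into an 18-month trial. The term well-tolerated in sections 1.3 and 3.1 has no numeric definition, and section 8.3 gives no error rates for 15 subjects. Section 1.3 explains that Phase 1 exists because most data at higher doses are not specific to the elderly.

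**Working it through.** **Inputs from the documents.** n = 15 (sections 3.1 and 3.1.1). A dose is excluded at 4 or more negative statements, so it is not excluded at 0 to 3 (sections 8.2, 9.6.1, 11.1). The protocol states no power or error rate for this rule, so there is no figure of its own to reproduce.

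**Inputs assumed.** The true share p who cannot take 1200 mg, and the share e of all subjects who are intolerant, stop before 1200 mg and make no counted statement about it. The documents give no value for e, so a range is shown.

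**Formula.** With X the number of counted refusals at 1200 mg, X is binomial (15, p − e). The chance that the rule triggers is P(X ≥ 4) = 1 − [P(0) + P(1) + P(2) + P(3)].

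**Illustration with p = 40%.**

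| Stop earlier, uncounted (e) | Counted refusal rate (p − e) | P(0)+P(1)+P(2)+P(3) | P(rule triggers for 1200 mg) |
|---|---|---|---|
| 0% | 40% | 0.0905 | 0.9095 (91%) |
| 5% | 35% | 0.1727 | 0.8273 (83%) |
| 10% | 30% | 0.2969 | 0.7031 (70%) |
| 20% | 20% | 0.6482 | 0.3518 (35%) |

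**Illustration with p = 25%.** Section 8.3 expects that about 25% of the Phase 2 ALA arm may not tolerate 1200 mg. Borrowing that rate, the rule triggers with probability 1 − 0.4613 = 0.54 if all are counted, 1 − 0.6946 = 0.31 if a quarter of the intolerant stop earlier (counted rate 18.75%), and 1 − 0.8922 = 0.11 if half do (12.5%).

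**Worst case by counting.** Suppose each stopper states a refusal only of the dose just taken: 3 at 600 mg, 3 more at 800 mg and 3 more at 1200 mg. Then 3 + 3 + 3 = 9 of 15 (60%) cannot take 1200 mg, and no dose reaches 4 statements.

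**Effect on the proportion among those asked.** The threshold is 4/15 = 26.7%. If 5 subjects stop early and 3 of the remaining 10 refuse 1200 mg, 30% of those asked have refused. The dose is still not excluded, although 5 + 3 = 8 of 15 (53%) cannot take it.

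**The case against.** The strongest reply is that the protocol is silent on this and does not exclude early stoppers. The question is hypothetical: a subject can say that 18 months at a dose is unimaginable without having taken it. The physician contacts every subject after each 5-day step, and the fixed 15 is compatible with asking all of them. If all stoppers were asked and said no, the gap would close. This stands as far as it goes. It would be wrong to write that early stoppers are never asked. But nothing requires that they be asked, and a physician-initiated stop calls for no statement.

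Second, the rule only excludes. Three or fewer refusals do not admit a dose. Use of 1200 mg also depends on its being well-tolerated, adverse events are the Phase 1 primary endpoint, results go to the IRB before Phase 2, and a Data and Safety Monitor independently reviews adverse events. This also stands: nine subjects stopping or refusing would be visible. None of these checks has a numeric criterion, however, and the percentage sent to the IRB has the same undefined divisor.

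Third, sections 1.2.2 and 12.1 place the main gastrointestinal effects at 1200 mg or higher, so most intolerance may appear where subjects are asked. That favours the smaller losses in the table, such as 91% to 83%.

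A reader might infer that a dose most subjects cannot take would probably get through. The documents do not support that. It requires at least 5 uncounted early stoppers. With 40% intolerant and 20% stopping early, the chance that 8 or more of 15 are intolerant while 3 or fewer refuse at 1200 mg is 6.4%; with 10% stopping early it is 0.4%. A reader might also infer that the per-dose adverse-event percentages are diluted. That follows only if 15 is the divisor at every dose, and section 8.1 names none.

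**Conclusion.** The point holds as a gap in a stated decision rule with a known direction of bias. Applied literally, the rule keeps early stoppers in the 15 without letting them count against the doses they did not reach, so it is less likely to exclude a higher dose than its threshold suggests. At an assumed 40% intolerance, the loss in trigger probability runs from 8 percentage points (91% to 83%) to 56 (91% to 35%) as early stopping rises from 5% to 20% of subjects. The 9-of-15 case is an extreme, not an expectation.

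The size rests on the assumed intolerance and stopping rates, on independence between subjects, and on stoppers giving no counted answer for later doses. The finding does not show that the count alone settles the Phase 2 dose, and it says nothing about which dose is suitable. The correction should be made because it is cheap and the criterion has no numeric backup.

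**What to change.** Reconcile the counting rule in sections 8.2, 9.6.1 and 11.1 with the stopping provisions in 3.1, 6.2, 9.6.1 and 11.1, and align the wording of 3.1.1 with conditional escalation:

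- Define numerator and denominator on the same subjects for each dose, and say whether stoppers are replaced and whether they are asked about doses not reached.
- State in advance that an answer missing because the subject stopped, or was stopped, at or before a dose is not scored as tolerance of that dose, and state which count governs.
- Report the count to the IRB both with and without early stoppers.
- In section 8.1, give per-dose adverse-event percentages over the number who took that dose.

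The threshold of 4 is left unchanged and no dose is proposed; the choice of counting convention is for the sponsor. The cost is a few sentences, with no added subjects or visits. The downside is that a dose may be somewhat more likely to meet the exclusion rule.

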10.1 Confidentiality

Information about study subjects will be kept confidential and managed according to the requirements of the Health Insurance Portability and Accountability Act of 1996 (HIPAA). Those regulations require a signed subject authorization informing the subject of the following:

- What protected health information (PHI) will be collected from subjects in this study
- Who will have access to that information and why
- Who will use or disclose that information
- The rights of a research subject to revoke their authorization for use of their PHI.

In the event that a subject revokes authorization to collect or use PHI, the investigator, by regulation, retains the ability to use all information collected prior to the revocation of subject authorization. For subjects that have revoked authorization to collect or use PHI, attempts should be made to obtain

CONFIDENTIAL

permission to collect at least vital status (i.e. that the subject is alive) at the end of their scheduled study period.

10.2 Data Collection and Management

Phase 1: For the ALA tolerability test, data will be entered onto case report forms by the Research Coordinator or Physician Investigator. There will be no electronic records for the tolerability test.

Phase 2: Data will be directly collected onto case report forms in real time by the study-certified clinic coordinator or examining ophthalmologist. The case report forms will be considered the source data. Data will be entered by study certified clinic coordinators into a central database using the Research Electronic Data Capture (REDCap) system.⁵⁵ REDCap is a secure, web-based application designed to support data capture for research studies, providing 1) an intuitive interface for validated data entry; 2) audit trails for tracking data manipulation and export procedures; 3) automated export procedures for seamless data downloads to common statistical packages; and 4) procedures for importing data from external sources.

Clinical examination data are recorded directly onto the CRFs during the clinic visit and are considered the source documentation. Each item entered by the clinic coordinator is checked for valid codes, legitimate ranges, legal dates, etc. and invalid entries are flagged. Validation of data occurs during and after the data entry session. Electronic logs of the completion status of each form and assessment are tracked by the Coordinating Center to determine the status of data collection for each registered participant. Form revisions and additions are accommodated by having data management staff at the Sponsor modify or create the appropriate data definition.

Data that have been entered into REDCap are subject to additional consistency checking involving more complex logic than implemented during data entry checking. Often these post-entry checks involve several different forms and visits. The Center for Preventive Ophthalmology and Biostatistics (CPOB) biostatistician will develop the logic for these checks and the comments to be associated with the resulting data queries. The Clinic Coordinator reviews edit messages and the corresponding data forms. If necessary, the Clinic Coordinator corrects the paper form, initials and dates the form, and updates the online database. The updated data records are again subjected to the entire data checking system. When extraordinary circumstances arise in which the query may never be able to be resolved to meet the requirements of the edit logic, the biostatistician may, with the approval of the Director, flag specific items on specific forms as exempt from further edit. The REDCap system generates an entry into a log of changes after every record correction so that a fully verifiable audit trail is created.

Records Retention

REDCap databases are backed up on a regularly scheduled basis. The backup data files are kept in a secured environment and are available for recovery. Data files that reside on the CPOB file server are backed up nightly. In addition, all CPOB personnel are required to keep copies of key documents such as forms, correspondence, and reports on the file server, which is on an automatic backup schedule. Files of the data system as of the time of each data freeze and for each publication are also archived.

11 Study Monitoring, Auditing, and Inspecting

11.1 Study Monitoring Plan

Phase 1: After a subject has taken a study dose for 5 days, a study physician will contact the subject and do a complete review of systems to document any adverse events. Symptoms reported will be graded as mild, moderate, or severe and this data will be recorded. If a subject does not feel comfortable proceeding to the next higher dose, then that subject will stop participation in the study at that point. If after review of the adverse event(s) (and their quality) that a subject experienced at a particular dose, then the study physician also may stop the subject's participation in the study if there is any safety concern. If 4 or more (out of 15) subjects state that they could not imagine taking a particular dose for 18 months, then that dose will not be used in the Phase 2 Trial.

CONFIDENTIAL

Phase 2: Both the Sponsor and the Principal Investigators ensure safety and compliance. There will be a Data and Safety Monitor (DSM). A Data Safety Monitoring Plan has been developed based on risk. At this time there is no Data Safety Monitoring Board as this is low risk study.

The Investigators will allocate adequate time for monitoring with regards to accurate and confidential record keeping, appropriate reporting of adverse events by all sites, The investigators will ensure that the monitor or other compliance or quality assurance reviewer is given access to all the above noted study-related documents and study related facilities (e.g. pharmacy, diagnostic laboratory, etc.), and has adequate space to conduct the monitoring visit.

